8.2.3 Vital Signs

8.2.3.1 Blood Pressure and Pulse Rate

At each clinic visit, BP and pulse rate should be taken using a standard sphygmomanometer after the participant has rested in a supine position for at least 5 minutes (10 minutes when supine BP and pulse rate measurements are followed by orthostatic BP evaluation).

On all dosing days, BP and pulse rate are to be assessed prior to any blood draw and IP administration and repeated 5 ± 5 minutes after completion of IP administration. Additional measurements of supine BP and pulse rate will be taken on Day 1 at the following time points: 30 ± 5 minutes, 60 ± 10 minutes, 2 hours ± 10 minutes, and 4 hours ± 10 minutes after the start of IP administration.

8.2.3.2 Orthostatic Blood Pressure Measurements and Follow-up of Confirmed Orthostatic Hypotension

Orthostatic BP measurements will be obtained at all clinic visits using a standard sphygmomanometer and taken after scheduled supine measurements (1 and 3 minutes after the participant stands) and prior to any required blood draw or IP administration (and prior to randomisation on Day 1).

To minimise chances of orthostatic hypotension related to volume depletion, participants should be well hydrated when they come to the clinic for study visits. Investigators should advise that participants drink 8 to 16 ounces (240 to 480 mL) of water prior to reporting for the study visit.

Supine BP measures will be collected after participants have been lying down for at least 10 minutes. To ensure that a stable supine BP is obtained, at least 2 systolic and 2 diastolic BP measurements will be obtained. If the replicate measurements differ by no more than 10 mmHg and 5 mmHg, respectively, the supine BP will be considered stable. The mean value of each replicate (mean systolic and mean diastolic value) will represent the baseline BP for that visit. After stable BP is achieved, the participant will stand and a BP measurement will be taken at 1 and 3 minutes after the participant stands. If the BP measurements do not meet the criteria for orthostatic hypotension, no additional measurement is needed (refer to exclusion criterion 43 for screening visit and Visit 2 assessments and Table 6 for the assessments after Visit 2). If BP measurements taken at the screening visit or Visit 2 meet exclusion criterion 43, then the participant is not eligible for participation in the study. After Visit 2 (Day 1), if the initial BP measurement meets any of the criteria shown in Table 6, investigators will repeat the supine and standing measurements up to 2 additional times.

Mean supine systolic BP	Decrease in BP indicative of orthostatic hypotension	Actions for both criteria			
\leq 150 mmHg	$\geq 20 \text{ mmHg systolic or}$ $\geq 10 \text{ mmHg diastolic}$	Repeats the BP measurements (supine and standing) up to 2 additional times.			
> 150 mmHg	≥ 30 mmHg systolic or ≥ 15 mmHg diastolic	 If either the 1 minute or 3 minute standing BP meets the orthostatic (postural) hypotension criteria, then the sequence is considered indicative of orthostatic hypotension. If 2 of 2 or 2 of 3 sequences are positive, then orthostatic hypotension is confirmed and an AE of orthostatic hypotension will be reported. 			

 Table 6
 Orthostatic Blood Pressure Criteria and Management

AE, adverse event; BP, blood pressure

Blood pressure changes meeting the prespecified criteria and confirmed as described above will be designated as a confirmed orthostatic hypotension episode. The event should be

reported as an AE whether or not the participant had accompanying symptoms. If a confirmed case of orthostatic hypotension occurs, the participant should be evaluated as soon as possible by a neurologist or cardiologist in order to determine the presence of sympathetic autonomic neuropathy. The participant should **not** receive further administration of IP until absence of sympathetic neuropathy is confirmed.

- ✓ If sympathetic neuropathy is confirmed, administration of IP will be permanently discontinued, and the participant will be asked to complete the assessments at the ET visit (Week 12 assessments) and then to enter the FU period (Section 7.1.2).
- ∀ If sympathetic neuropathy is not confirmed and orthostatic hypotension is not symptomatic, the participant can continue in the study as planned provided no more than 28 days passed since last IP administration (Section 7.1.3).
- ✓ If sympathetic neuropathy is not confirmed but orthostatic hypotension remains symptomatic for more than 14 days, administration of IP will be permanently discontinued, and the participant will be asked to complete the assessments at the ET visit (Week 12 assessments) and then to enter the FU period (Section 7.1.2).

Refer to the SoA (Table 1) for assessments to be performed at the ET visit and the FU period and Section 7.1.2 for procedures for early discontinuation of IP.

8.2.3.3 Blood Pressure Measured by an Ambulatory Blood Pressure Monitoring Device

Participants will be given training at their local study site about how to set up and apply the ABPM device. In brief, an appropriate size cuff encircling 80% to 100% of the arm will be selected and the device will be fitted to the nondominant arm of the participant, with the bladder placed over the artery, and an initial test reading performed. The participants will be advised that for the first reading the device will inflate to a pressure of 180 mm Hg, and thereafter the device will adapt to inflate to a pressure just above the last recorded BP. The participant will be advised to undergo normal daily activities while wearing the cuff, and he/she will be advised to avoid any strenuous form of activity, bathing, or showering while wearing the cuff. The participant will be advised to remain still during a measurement with the arm relaxed at heart level. The participant will also be given advice on how to wear the device during the day and at night while sleeping, and what to expect in terms of frequency of readings during the day (every 15 minutes) and overnight (every 30 minutes). During ABPM, systolic BP, diastolic BP, pulse pressure, pulse rate, and mean arterial pressure readings will be recorded over a period of 24 hours.

Participants will wear the ABPM device for a period of 24 hours at 2 separate times during the study: one time during the screening period and one time during the double-blind treatment period (between Weeks 8 and 12) (Table 1). Participants will receive the ABPM device at the study site, and training will be provided. The participant will wear the monitor/cuff for approximately 24 hours (including overnight at home) and will remove the device at home at

the end of the 24-hour period. Participants will return the device to the clinic at their next scheduled study visit after completing the 24-hour ABPM measurement.

8.2.3.4 Body Temperature

Body temperature will be measured in degrees Celsius using an automated thermometer at the visits and times indicated in the SoA (Table 1).

Body temperature will be taken at all clinic visits. On all dosing days, vital signs (including body temperature) are to be assessed prior to any blood draw and IP administration (and prior to randomisation on Day 1) and repeated 5 ± 5 minutes after completion of IP administration. On Day 1, body temperature will also be assessed at the following time points: 30 ± 5 minutes, 60 ± 10 minutes, 2 hours ± 10 minutes, and 4 hours ± 10 minutes after the start of IP administration.

8.2.3.5 Respiratory Rate

Respiratory rate will be measured in breaths per minute by observation at the visits and times indicated in the SoA (Table 1).

Respiratory rate will be measured at all clinic visits. On all dosing days, vital signs (including respiratory rate) are to be assessed prior to any blood draw and IP administration (and prior to randomisation on Day 1) and repeated 5 ± 5 minutes after completion of IP administration. On Day 1, respiratory rate will also be assessed at the following time points: 30 ± 5 minutes, 60 ± 10 minutes, 2 hours ± 10 minutes, and 4 hours ± 10 minutes after the start of IP administration.

8.2.4 Electrocardiograms

At the visits and time points specified in the SoA (Table 1), a 10-second, 12-lead safety ECG will be obtained after 10 minutes of supine rest, using the study site's own ECG machines.

On Day 1, ECG recording will be performed 30 to 120 minutes prior to IP administration (and prior to randomisation) and 4 hours \pm 30 minutes after IP administration. On all other dosing days, ECG recording will be performed at 30 to 120 minutes prior to IP administration; thereafter, ECGs will be recorded at Week 12 and Week 32. ECG recording should be performed prior to any blood draw.

The investigator will judge the overall interpretation as normal or abnormal clinically nonsignificant or abnormal clinically significant, and this evaluation will be reported in the eCRF. Clinically significant findings should also be documented on the AE page of the CRF if applicable. The PI may add extra 12-lead resting ECG safety assessments, if needed. These assessments should be entered as an unscheduled assessment.

Cardiovascular findings that are considered to be potential indicators of sympathetic nervous system dysfunction should be evaluated by a cardiologist or neurologist as soon as possible. Such findings include but are not necessarily limited to significant bradycardia (defined as pulse rate of \leq 45 beats per minute on an ECG). (Note that this value is exclusionary at screening.)

8.2.5 Survey of Autonomic Symptoms (SAS)

The SAS is a validated, easily administered instrument to measure autonomic symptoms and has been proposed as a valuable tool in assessing autonomic neuropathies in clinical trials (Zilliox et al 2011).

The SAS scale evaluates the presence of symptoms and the degree of severity. The SAS consists of 11 questions in women and 12 questions in men. Each question has a Yes or No answer to symptoms occurring 6 months prior to IP administration. Questions answered with "Yes" are further rated from 1 to 5 by asking the participant how much each symptom is bothering him or her. Each answer is scored on a scale from 1 to 5 where 1 = not at all and 5 = a lot, and a total symptom impact score is determined.

The questions in the questionnaire assess the following domains: orthostatic, sudomotor symptoms, vasomotor, gastrointestinal, urinary, and sexual dysfunction.

Participants will complete the SAS at the times indicated in the SoA (Table 1).

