After the end-of-treatment (EOT) visit at Week 12, participants will enter the FU period, which comprises 3 clinic visits (Weeks 18, 32, and 36) and 4 FU phone calls (Weeks 15, 21, 24, and 28). All participants who receive IP are expected to complete the FU period.

Interim Analysis

The study incorporates 2 interim analyses: (1) a futility analysis will take place when approximately 25% of participants are evaluable for the primary endpoint; this analysis will assess the likely success of the study outcome and will enable the sponsor to make a go/no-go decision regarding continuation of the study; and (2) an interim analysis of efficacy data will take place when approximately 50% of participants are evaluable for the primary endpoint; this analysis will enable the sponsor to plan future project-related activities, but without making any changes to the current study.

No alpha adjustment is required for the interim analyses because early stopping for efficacy is not a feature of the study design.

Disclosure Statement

This is a Phase IIb, randomised, parallel-group, placebo-controlled, double-blind treatment study of MEDI7352 with 5 cohorts that are participant- and investigator-blinded.

Number of Subjects

This is a multinational, multicentre, interventional study in which approximately 350 eligible participants will be randomly assigned to the IPs (one of 4 dose levels of MEDI7352 or placebo).

Intervention Groups and Duration

Screening period: up to 45 days

Randomisation: participants will be randomised in a ratio of 1:1:1:1:1, respectively, to one of the following 5 treatment cohorts:

- ∀ Cohort 1: CCI MEDI7352 Q2W administered CC
- ∀ Cohort 2: CCI MEDI7352 Q2W administered CC
- ∀ Cohort 3: CCI MEDI7352 Q2W administered CC
- ∀ Cohort 4: CCI MEDI7352 Q2W administered
- ∀ Cohort 5: Placebo to match MEDI7352 Q2W administered ^{CC}

Treatment period: 12 weeks with 6 fixed doses of IP administered at Weeks 0 (Day 1), 2, 4, 6, 8, and 10 and an EOT visit conducted at Week 12

FU period: 24-week FU period with a final FU visit at Week 36 (\pm 7 days)

The maximum study duration for each participant is approximately 50 weeks. The overall study duration is expected to be 31 months (18 months of active screening and enrolment, 11 months of treatment and FU, and 2 months for database lock).

Data Monitoring Committees:

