Clinic visit (V)	V1	V2	V3	V4 ^f	V5 f	V6	V 7	V8	V9	V10	V11	Phone call 1	V12	Phone calls 2, 3, & 4	V13	V14
WOMAC (pain, stiffness, and function subscales) ⁿ		x		х	х	х	х	х			Xe		х			
PGA ⁿ		Х		Х	Х	Х	Х	Х			Xe		Х			
CCI																
Safety assessments		1							1			1				
Physical and neurological examination	х	x		Х	х	х	Х	х			х		Х		Х	х
12-lead ECG °	Х	Х		Х	Х		Х	Х			х				Х	
24-hour ABPM ^p	Day -14 ^a							Х								
Total neuropathy score- nurse	Х	x		Х	х	х	х	х			Х				Х	
Survey of autonomic symptoms		x														х

			Double-blind treatment period (12 weeks)										ow-up per (24 weeks			
Study week	Screening/ baseline ^a	Wk 0°	Wk 1 ± 3 d ^d	Wk 2 ± 3 d	Wk 4 ± 3 d	Wk 6 ± 3 d	Wk 8 ± 3 d	Wk 10 ± 3 d	Wk11 ± 3 d ^d	Wk 11 ± 3 d ^d	(EOT or ET °) Wk 12 ± 3 d	Wk 15 ± 3 d	Wk 18 ± 7 d	Wk 21, 24, & 28 ± 3 d	Wk 32 ± 7 d	Wk 36 ± 7 d
Study day	Day -45 to -1	D 1	D 7	D 14	D 28	D 42	D 56	D 70	D 74	D 77	D 84	D 105	D 126	D 147, 168, & 196	D 224	Day 252
Clinic visit (V)	V1	V2	V3	V4 f	V5 f	Vó	V 7	V 8	V9	V10	V11	Phone call 1	V12	Phone calls 2, 3, & 4	V13	V14
Vital signs (BP and pulse rate [supine], respiratory rate, and body temperature) ^q	X	x	x	x	х	x	х	x	х	x	x		х		х	x
Orthostatic BP ^r	Х	Х	Х	Х	Х	Х	Х	Х	Х	Х	Х		Х		Х	х
Injection site assessment ^s		x		х	Х	х	Х	х								
Adverse events	Х	Х	Х	Х	Х	Х	Х	Х	Х	Х	X	Х	Х	Х	Х	X
Laboratory assessments																
Urine collection for:																
Drug screen	Xa			Х												
Urinalysis	Х	Х		Х	Х	Х	Х	Х			Х				Х	
Pregnancy tests ^t		X		Х	Х	Х	Х	Х								х
CCI																
Blood collection for:																
Haematology, chemistry, and coagulation ^v	х	х		х	х	х	х	х			х				х	

					Doubl	e-blind tr (12 v	reatment veeks)	period						ow-up per (24 weeks		
Study week	Screening/ baseline ^a	Wk 0 ^c	$Wk 1 \\ \pm 3 d^d$	Wk 2 ± 3 d	Wk 4 ± 3 d	Wk 6 ± 3 d	Wk 8 ± 3 d	Wk 10 ± 3 d	Wk11 ± 3 d ^d	Wk 11 $\pm 3 d^d$	(EOT or ET ^c) Wk 12 ± 3 d	Wk 15 ± 3 d	Wk 18 ± 7 d	Wk 21, 24, & 28 ± 3 d	Wk 32 ± 7 d	Wk 36 ± 7 d
Study day	Day -45 to -1	D 1	D 7	D 14	D 28	D 42	D 56	D 70	D 74	D 77	D 84	D 105	D 126	D 147, 168, & 196	D 224	Day 252
Clinic visit (V)	V1	V2	V3	V4 ^f	V5 ^f	V6	V7	V8	V9	V10	V11	Phone call 1	V12	Phone calls 2, 3, & 4	V13	V14
Serology (HIV, hepatitis B, hepatitis C, and tuberculosis [QuantiFERON])	X															
Serum pregnancy test	X ^a															
Haemoglobin A1c	Х														Х	
ACPA antibodies	Х															
FSH test screening for women < 50 years	Х															
Immunogenicity (ADA) sampling		Xw	Х	Xw	Xw	Xw	Xw	Xw	Х	Х	X x		Х		Х	

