PK analysis		Xw	Х	Xw	Xw	Xw	Xw	Xw	Х	Х	X ^x		Х		Х	
PD and exploratory biomarkers:																
PD: free NGF		Xw	Х	Xw	Xw	Xw	Xw	Xw	Х	Х	X ^x		Х		Х	
PD: total NGF		Xw	Х	Xw	Xw	Xw	Xw	Xw	Х	Х	X ^x		Х		Х	
PD: CXCL13		Xw	Х	Xw	Xw	Xw	Xw	Xw	Х	Х	X ^x		Х		Х	

			(12 weeks) (2									ow-up per (24 weeks	riod ^b			
Study week	Screening/ baseline ^a	Wk 0°	Wk 1 ± 3 d ^d	Wk 2 ± 3 d	Wk 4 ± 3 d	Wk 6 ± 3 d	Wk 8 ± 3 d	Wk 10 ± 3 d	Wk11 ± 3 d ^d	Wk 11 ± 3 d ^d	(EOT or ET °) Wk 12 ± 3 d	Wk 15 ± 3 d	Wk 18 ± 7 d	Wk 21, 24, & 28 ± 3 d	Wk 32 ± 7 d	Wk 36 ±7 d
Study day	Day -45 to -1	D 1	D 7	D 14	D 28	D 42	D 56	D 70	D 74	D 77	D 84	D 105	D 126	D 147, 168, & 196	D 224	Day 252
Clinic visit (V)	V1	V2	V3	V4 ^f	V5 f	Vó	V 7	V8	V9	V10	V11	Phone call 1	V12	Phone calls 2, 3, & 4	V13	V14
Other assessments																
Dispense rescue medicine ^z	x	x	x	x	x	x	x	x		x	x					
Record rescue medication use ^z	Day -14 —	•								•						
Return rescue medication/check compliance ^{aa}		x	х	х	х	x	х	x	x	x	x		х			
Start standard-of-care treatment bb													Х			
COVID-19 symptom screening ^{cc}		x		х	х	х	х	x								

			Double-blind treatment period (12 weeks)								Follow-up period ^b (24 weeks)					
	Screening/		Wk 1	Wk 2	Wk 4	Wk 6	Wk 8	Wk 10	Wk11	Wk 11	(EOT or ET ^e) Wk 12	Wk 15	Wk 18	Wk 21, 24, & 28	Wk 32	Wk 36
Study week	baseline ^a	Wk 0 ^c	$\pm 3 d^{d}$	± 3 d	± 3 d	± 3 d	± 3 d	± 3 d	$\pm 3 d^d$	$\pm 3 d^{d}$	± 3 d	± 3 d	± 7 d	± 3 d	± 7 d	± 7 d
Study day	Day -45 to -1	D 1	D 7	D 14	D 28	D 42	D 56	D 70	D 74	D 77	D 84	D 105	D 126	D 147, 168, & 196	D 224	Day 252
Clinic visit (V)	V1	V2	V3	V4 ^f	V5 ^f	V6	V7	V8	V9	V10	V11	Phone call 1	V12	Phone calls 2, 3, & 4	V13	V14
COVID-19 nose and/or throat/saliva swab (SARS-CoV-2- test) ^{cc, dd}		X		Х	Х	X	Х	Х								
CCI	1	1	1		1	1	1			1	1	1	1			

- For participants who discontinued IP early, the 3 FU clinic visits and 4 phone calls will occur at the times indicated below (Section 7.1.2):
 - ! FU visit 1: Corresponds to Week 18; to be performed 8 weeks after the last IP administration
 - ! FU visit 2: Corresponds to Week 32; to be performed 22 weeks after the last IP administration
 - ! FU visit 3: Corresponds to Week 36; to be performed 26 weeks after the last IP administration
 - ! FU phone calls 1, 2, 3, and 4: Corresponds to Weeks 15, 21, 24, and 28, respectively; to be conducted 5, 11, 14, and 18 weeks after the last IP administration, respectively

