Participants who discontinue IP early will be asked to complete study assessments at the ET visit (ie, Week 12 assessments) as soon as possible and then to enter the FU period.

Participants who discontinue IP prematurely may be given standard-of-care therapy for their pain after the ET visit as deemed appropriate by the investigator and in alignment with local guidelines/label (including paracetamol, aspirin, NSAIDs, and COX-2 inhibitors if deemed necessary). However, initiation of NSAIDs, COX-2 inhibitors, and aspirin (in doses that exceed 325 mg/day) is prohibited until after 5 half-lives following the last IP administration (ie, approximately 3 weeks). Note that it is recommended to postpone NSAIDs/COX-2 inhibitors intake until 8 weeks after the last IP administration. In addition, initiation of corticosteroid therapy (eg, intra-articular injections) should be deferred until at **least 8 weeks** after the last IP administration.

Refer to the SoA (Table 1) for assessments to be performed at the ET visit and FU period. All participants prematurely discontinued from IP are expected to complete the ET visit and the 24-week FU period, which consists of 3 FU clinic visits and 4 phone calls at the times indicated below:

- ∀ ET visit: Week 12 assessments to be performed as soon as possible after the last IP administration. The following assessments/procedures will not be performed beyond the ET visit:
 - # Daily NRS pain score
 - # DSIS
 - # Rescue medication recording
 - # WOMAC
 - # PGA
 - # Blood collection for PK, ADA, and PD biomarkers
- ∀ FU phone call 1: To be conducted 5 weeks after the last IP administration
- ∀ FU visit 1: Week 18 assessments to be performed 8 weeks after the last IP administration
- ∀ FU phone call 2: To be conducted 11 weeks after the last IP administration
- ∀ FU phone call 3: To be conducted 14 weeks after the after the last IP administration
- ∀ FU phone call 4: To be conducted 18 weeks after the last IP administration
- ∀ FU visit 2: Week 32 assessments to be performed 22 weeks after the last IP administration
- ∀ FU visit 3: Week 36 assessments to be performed 26 weeks after the last IP administration

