All participants must stop taking their current pain medication for at least 48 hours or 5 halflives, whichever is longer, prior to the start of the daily NRS pain score baseline period on Day -7. Half-lives of commonly used pain medications are shown in Appendix K. The list is not all-inclusive. The Physician's Desk Reference provides half-life information.

Double-blind Treatment Period

The following procedures will be performed on Day 1 prior to randomisation:

- \forall Inclusion and exclusion criteria confirmation
- ∀ Urine pregnancy test (for women who are not surgically sterile only; the results must be negative in order to proceed with IP administration)
- ∀ Urine samples for biomarkers (fasting) should be from the second morning void of the day or after. Refer to Section 8.6.1.4 for additional information.
- ∀ Daily pain diary (NRS)
- ∀ DSIS
- ∀ TNSn
- ∀ Physical and neurological examination
- ∀ Supine BP and pulse rate (prior to any blood draw)
- ∀ Orthostatic BP (after supine BP, 1 and 3 minutes after the participants stands and prior to any blood draw)
- ∀ Body temperature (prior to any blood draw)
- ∀ Respiratory rate (prior to any blood draw)
- ∀ ECG (30 to 120 minutes prior to IP administration and prior to any blood draw)
- ∀ Urinalysis

The following procedures will be performed on Day 1 after randomisation but prior to administration of IP:

- \forall WOMAC index
- ∀ PGA
- ∀ CCI
- ∀ Survey of Autonomic Symptoms (SAS)
- ∀ Blood collection for haematology, chemistry, coagulation, PK, ADA, PD, CCI

The following procedures will be performed on Day 1 after randomisation and administration of IP:

- \forall ECG will be performed 4 hours \pm 30 minutes after IP administration.
- ✓ Supine BP and pulse rate measurements will be performed at 5 ± 5 minutes after completion of IP administration, and 30 ± 5 minutes, 60 ± 10 minutes, 2 hours ± 10 minutes, and 4 hours ± 10 minutes after the start of IP administration.
- ∀ Body temperature measurements will be performed at 5 ± 5 minutes after completion of IP administration, and 30 ± 5 minutes, 60 ± 10 minutes, 2 hours ± 10 minutes, and 4 hours ± 10 minutes after the start of IP administration.
- \forall Respiratory rate measurements will be performed at 5 ± 5 minutes after completion of IP administration, and 30 ± 5 minutes, 60 ± 10 minutes, 2 hours ± 10 minutes, and 4 hours ± 10 minutes after the start of IP administration.

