9.4.3.6 Other Safety Endpoint(s)

Findings from other safety assessments (TNSn and injection site reactions) will be listed and may be summarised if warranted.

The SAS scores will be summarised by treatment group for the total number of symptoms reported and the total impact score. The summary will be presented by visit and will include the change from baseline.

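### The Survey of Autonomic Symptoms is given only before the first dose and at Week 36, so its change from baseline describes mainly off-drug time, and its recall wording does not fit a post-treatment visit

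*Protocol*

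**What the plan says.** Section 8.2.5 defines the survey's recall: "Each question has a Yes or No answer to symptoms occurring 6 months prior to IP administration". It leaves timing to the schedule: "Participants will complete the SAS at the times indicated in the SoA (Table 1").

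In the Section 1.3 schedule, the row "Survey of autonomic symptoms" carries two marks, at Week 0 and at Week 36, and none between them. The Week 0 mark agrees with Section 8, which lists the SAS under the heading "The following procedures will be performed on Day 1 after randomisation but prior to administration of IP". The second mark sits in the same last column as the urine pregnancy test that footnote t places at Week 36.

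Dosing is set out in the Synopsis: "Treatment period: 12 weeks with 6 fixed doses of IP administered at Weeks 0 (Day 1), 2, 4, 6, 8, and 10". For early discontinuers, footnote b of the schedule says: "FU visit 3: Corresponds to Week 36; to be performed 26 weeks after the last IP administration".

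Section 9.4.3.6 commits to summarising the SAS by treatment group, for number of symptoms and total impact score: "The summary will be presented by visit and will include the change from baseline".

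**The concern.** Section 2.3.1.1 names autonomic neuropathy and sympathetic dysfunction as a potential risk of the anti-NGF mechanism. For another anti-NGF antibody it cites observation-time adjusted rates of sympathetic-dysfunction events of 20.3% on placebo, 29.1% on 2.5 mg and 46.2% on 5 mg. It also reports the regulator's overall conclusion that no increased risk was found. On the protocol's own account, then, this is something to be measured. The SAS is a listed safety endpoint.

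The survey has one post-baseline administration, and that administration falls long after dosing has stopped. If autonomic symptoms rise on drug and resolve when it is withdrawn, the by-arm SAS change from baseline could show little difference from placebo. A reader of the study report could take that as evidence about the treatment period, when it mostly describes follow-up.

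**Working it through.** **Inputs.** First dose Day 1 and last dose Week 10 (Day 70): Synopsis and schedule. End of treatment Week 12 (Day 84, ±3 days) and final visit Week 36 (Day 252, ±7 days): schedule. Recall of 6 months: Section 8.2.5. Five half-lives of about 3 weeks: Section 7.1.2, where certain analgesics are "prohibited until after 5 half-lives following the last IP administration (ie, approximately 3 weeks"). Assumption: 6 months is 182 days, with a range of 180 to 184.

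**Reproducing the protocol's interval.** Week 36 − Week 10 = 26 weeks. Day 252 − Day 70 = 182 days, and 182 / 7 = 26 weeks. This matches the 26 weeks that footnote b gives for early discontinuers.

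**What the Week 36 survey covers, by reading of Section 8.2.5.**

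1. *Literal reading (before IP administration).* The Week 36 form asks again about the pre-treatment period. No treatment time is covered.
2. *The sentence describes only the Day 1 form.* The Week 36 recall is then undefined in the protocol.
3. *Six months before the visit.* The look-back starts on Day 252 − 182 = Day 70.
   - First-to-last-dose span (Day 1 to Day 70, 69 days): 0 days covered.
   - Treatment period to Day 84: 84 − 70 = 14 days, and 14 / 84 = 17%. These are Weeks 10 to 12.
   - With the final visit on Day 245 to 259, the last dose on Day 67 to 73 and a recall of 180 to 184 days, coverage is 0 to 12 days of the first-to-last-dose span. For the treatment period it is 5 / 84 = 6% to 23 / 84 = 27%.
   - Early discontinuers: the visit is 26 weeks after the last dose, so the look-back again starts at about the last dose.
   - Recall time later than five half-lives after the last dose: (26 − 3) / 26 = 23 / 26 = 88%.

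The Day 1 window lies wholly before treatment. On none of the three readings are Weeks 0 to 10 nominally covered.

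**What a Week 12 survey would cover with the same recall length.** Day 84 − 182 = −98, so the window opens about 98 / 7 = 14 weeks before the first dose and spans all 84 treatment days. Treatment-period time would be 12 / 26 = 46% of the recall, against 2 / 26 = 8% at Week 36. The 14 pre-dose weeks are also inside the Day 1 recall. Some answers will therefore repeat, but a change from No on Day 1 to Yes at Week 12, if recalled correctly, has to come from the time after the first dose.

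**The case against.** The strongest objection is that autonomic effects are monitored during treatment by other means:

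- Orthostatic blood pressure is taken at every clinic visit (Section 8.2.3.2), and the incidence of orthostatic hypotension is summarised (Section 9.4.3.3).
- ECGs are recorded on treatment, with a bradycardia criterion (Section 8.2.4).
- Anhidrosis and hypohidrosis are asked about at the neurological examinations (Section 8.2.2).
- The TNSn includes autonomic symptoms (Section 8.2.8).
- Adverse events are collected at each visit and tabulated by arm (Sections 8.3.6 and 9.4.3.1).

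This stands for orthostatic and sudomotor effects. A reader might infer that the trial as a whole would give false reassurance on autonomic safety. The documents do not support that, and the risk attaches to the SAS summary alone. The objection does not close the gap entirely. The SAS also asks about vasomotor, gastrointestinal, urinary and sexual symptoms, and the protocol describes no other scheduled autonomic instrument for those domains. It does not say which symptoms the TNSn item covers, and Section 9.4.3.6 promises only a listing of TNSn findings, with a summary if warranted.

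A second objection is that the protocol never states what the Week 36 form asks, since the questionnaire is not reproduced. That is fair. The Day 70 start and the 88% depend on the visit-anchored reading. The uncertainty is itself part of the defect.

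Third, a Week 36 survey can still show persistent or late symptoms. That is a reason to keep it, but it does not make it an on-treatment measure.

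Fourth, the summary is descriptive with no test, and autonomic dysfunction is not among the adverse events of special interest in Section 8.3.5. This limits the weight of the point.

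**Conclusion.** The point holds for the SAS endpoint. The recall wording in Section 8.2.5 does not fit the Week 36 visit. On a visit-anchored reading with 6 months taken as 182 days, the only post-baseline survey nominally covers none of the span from first to last dose. It covers 14 of 84 treatment-period days (17%; 6% to 27% across windows and recall length), and it mixes those days with follow-up in a single answer. The planned change from baseline therefore describes mainly off-drug time and could miss a reversible rise.

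A reader might go further and say that the survey cannot measure on-treatment symptoms at all. That is too strong: Weeks 10 to 12 belong to the protocol's 12-week treatment period and fall inside a visit-anchored recall, and visit windows can add up to 12 days of the dosing span.

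The SAP cannot repair this, because it can neither add a visit nor change what participants are asked.

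**What to change.** 1. Mark the SAS at the Week 12/ET visit in the Section 1.3 schedule. The TNSn and neurological examination are already done there.
2. Reword Section 8.2.5 so that recall is the 6 months before each survey. This keeps the same recall length at every administration, and at Week 12 it spans all dosing.
3. In Section 9.4.3.6, name the Week 12/ET change from baseline by arm as the on-treatment comparison, and keep Week 36 as the follow-up comparison.

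A shorter post-baseline recall, such as the time since the first dose, is not advisable. It would differ from the baseline recall and would vary between completers and early stoppers.

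The cost is one questionnaire of 11 items (women) or 12 items (men) at an existing visit, plus a schedule mark and a wording change. The downside is that a 6-month recall at Week 12 also takes in about 14 pre-dose weeks. That is the same in all arms for completers. Early stoppers would have more pre-dose time in the window. For example, an ET visit 2 weeks after the first dose would carry 26 − 2 = 24 pre-dose weeks, so time on study should be shown beside the ET results.
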